13.6 APPENDIX IV: URINE PROTEIN TO CREATININE (UPC) RATIO

Clinical Meaning of UPC

There is a good correlation between the ratio of urine protein to urine creatinine concentrations (UPC) in a random urine sample and the amount of protein excreted in a 24-hour urine collection period. ⁴⁸ Thus, the UPC ratio from a single random urine sample permits estimation of the 24-hour urine protein excretion. The creatinine excretion is fairly constant throughout the day regardless of changes in urine flow rate:

- Men excrete 20 mg to 25 mg of creatinine/kg of body weight/day
- Women excrete 15 mg to 20 mg of creatinine/kg of body weight/day
- Normal protein excretion is <100 mg to 150 mg per 24 hours.
- The UPC ratio is roughly equal to the 24-hour urine protein excretion in g/day

Calculating UPC Ratio

UPC ratio = (Urine protein [mg/dL]) / (urine creatinine [mg/dL]) = numerically equivalent to grams (g) protein excreted in urine over 24 hours.

Example: If a patient has a urine protein concentration of 90 mg/dL and urine creatinine concentration of 30 mg/dL,

then UPC ratio = $\frac{90(mg/dL)}{30 (mg/dL)} = 3$

UPC ratio of 3 correlates to roughly 3g of protein excretion in a 24-hour period.

Units for UPC ratio

UPC is a calculated ratio. The guidelines in the protocol are based on having urine protein and urine creatinine measured in the same units (e.g., mg/dL). The International System of Units (SI) units for urine protein and urine creatinine are not the same, so these must be converted to mg/dL before calculating the ratio. For reference, the conversion factors for commonly used units for protein and creatinine are provided below.

Starting units	Conversion to mg/dL
Protein (g/L)	Multiply by 100
Creatinine (µmol/L)	Divide by 88.4
Creatinine (mmol/L)	Multiply by 11.3

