Serum K⁺, Ca^{++} , Mg^{++} , phosphate levels should be monitored given the risk of prolonged QTc. If serum Ca^{++} is abnormal, ionized calcium should be obtained and interventions based on ionized calcium only.

Pazopanib should be held and an EKG obtained for

- Hypokalemia or hyperkalemia \geq Grade 2
- Hypocalcemia or hypercalcemia \geq Grade 3
- Hypophosphatemia or hyperphosphatemia \geq Grade 3
- Hypomagnesemia or hypermagnesemia \geq Grade 3

These laboratory values should be corrected as soon as possible in a manner consistent with good medical judgment. Pazopanib may be resumed at a reduced dose when:

- Hypokalemia or hyperkalemia is Grade 1 or within institutional limits
- Hypocalcemia or hypercalcemia is \leq Grade 2
- Hypophosphatemia or hyperphosphatemia is \leq Grade 2
- Hypomagnesemia or hypermagnesemia is \leq Grade 2.

Even though pazopanib administration is allowed at these lower laboratory toxicity grades, every effort should be made to correct the abnormal lab values to normal if possible.

5.4.5 Proteinuria:

- If urinalysis shows ≥ trace protein then obtain a urine protein: creatinine ratio (UPC).
- If the UPC is \geq 1, then obtain a 24-hour urine collection for protein estimation.
- If the urine protein is ≥ 3.5 g/24-hours then hold pazopanib and reassess urine protein weekly.
- If the urine protein decreases to < 3.5 g/24 hours in < 21 days then resume pazopanib at a reduced dose.
- Monitor the 24 hour urine protein or UPC weekly for 2 consecutive weeks once pazopanib is resumed.
- If pazopanib is held for ≥ 28 days then the patient must be removed from protocol therapy.
- 5.4.6 Cardiac Function:

5.4.6.1 Left Ventricular Systolic Dysfunction:

Adverse events & descriptions	Dose Modifications & Evaluations
LV EF <lln <math="" but="">\geq 50% OR</lln>	Continue drug and repeat Echo on Day 28 of
LV SF \leq LLN but \geq 24% without symptoms	subsequent cycle
of cardiac dysfunction	
LV EF 40 – 49% OR	Hold pazopanib and obtain repeat Echo in 7
LV SF 15 – 23% OR	days. If toxicity confirmed, then remove
Absolute decrease in SF \geq 8 percentage	from protocol therapy.
points from baseline	If not confirmed, then resume drug at reduced
	dose and repeat Echo 14 and 28 days after
	resuming pazopanib. If any 2 Echos
	demonstrate LV EF 40 - 49% OR LV SF 15 -
	23%
	$OR \ge 8$ percentage point decrease in SF then
	remove from protocol therapy and refer to
	pediatric cardiologist
Grade 3 LV EF decreased OR	Remove from protocol therapy – refer to

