Antineoplastic therapies since protocol therapy discontinuation ²⁰						Х

^{1.} Window for assessment is Day 25-28 of the preceding cycle for any assessment with the exception of disease evaluations. See footnote 12 for assessment window on disease evaluation.

- ³ Blood pressures will be measured with an appropriate sized cuff at rest. Blood pressure measurement will be repeated within the same day if the blood pressure (BP) is elevated (> the 95th percentile for age, height, and gender). If both BP measurements are > 95th percentile for age, height, and gender, follow the guidelines in Section 5.4.1. Patients with elevated BP (that is, BP greater than the 95th percentile for age, height, and gender) at any time should have BP measurements performed at least twice weekly until BP is within the 95th percentile for age, height, and gender (see Appendix V). Guidelines for the grading and management of hypertension are in Section 5.1.2.5, 5.4.1, and Appendix V.
- ⁴ Evaluations obtained for screening will ONLY be repeated at Cycle 1 Day 1 if they are older than 7 days.
- ⁵ If patients have Grade 4 neutropenia, then CBCs should be checked every 3 to 4 days until recovery to Grade \leq 3.
- ^{6.} If patients have Grade 3 or 4 thrombocytopenia, then CBCs should be checked twice a week until recovery to Grade ≤ 2 .
- ^{7.} If patient has LFT elevation, monitor LFTs as described in Section 5.4.3.

^{2.} Should be performed, if possible, at the time the patient comes off protocol therapy regardless of the reason, unless the test or procedure has been performed within the past 2 weeks.

- ^{8.} Patients found to have an abnormal TSH level at baseline and/or at subsequent visits should have a free T4 level measured (See Section 7.2.2). Management of hypothyroidism is described in Section 4.1.5.2.
- ^{9.} See Appendix IV for UPC rationale and calculation and Section 5.4.5 for dose modifications if UPC \geq 1. UPC assessment is adequate to follow-up prior proteinuria. If a 24-hour urine for protein is obtained, UPC is not required.
- ^{10.} A confirmatory disease evaluation should be obtained, if possible, on the next consecutive cycle after initial documentation of either a PR or CR. This confirmatory evaluation is in addition to the schedule as noted (eg: if confirmatory scans are done prior to Cycle 4, the next disease evaluation should be done as scheduled prior to Cycle 5)

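### Entry criterion 3.2.8.2c prints the 24-hour urine protein limit as a concentration (mg/dL), and Appendix IV converts UPC to grams per day without a body-size condition

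*Protocol*

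**What the plan says.** **Entry.** Protocol 3.2.8.2c accepts any one of three: a UPC below 1, a urinalysis negative for protein, or a 24-hour urine protein below 1000 mg/dL. It refers to Appendix IV. The opening note of 3.2 says that inclusion criteria are applied literally and are not waived. Under 3.2.1, patients are 1 to 18 years old.

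**On treatment.** Under 5.4.5, a UPC of 1 or more means the site must "then obtain a 24-hour urine collection for protein estimation". At 3.5 g/24 h or more it must "then hold pazopanib and reassess urine protein weekly". Drug resumes at a reduced dose if protein falls below 3.5 g/24 h in under 21 days.

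**Conversion.** Appendix IV (13.6) calls UPC "numerically equivalent to grams (g) protein excreted in urine over 24 hours". Its worked example concludes: "UPC ratio of 3 correlates to roughly 3g of protein excretion in a 24-hour period". It gives creatinine output per kilogram for adults only: "Men excrete 20 mg to 25 mg of creatinine/kg of body weight/day" and "Women excrete 15 mg to 20 mg of creatinine/kg of body weight/day". It sets no body-size condition.

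**Link.** Footnote 9 to the table in 7.1 reads "See Appendix IV for UPC rationale and calculation and Section 5.4.5 for dose modifications if UPC" is 1 or more, and then adds "UPC assessment is adequate to follow-up prior proteinuria".

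**The concern.** A 24-hour protein result is an amount per day. A limit in mg/dL cannot be compared with it unless urine volume is known, and the criterion names no volume. This is an eligibility threshold in a section that tells sites to take the text as printed. Taken so, it is much looser than the UPC alternative beside it. It could let in a patient who already meets the on-treatment hold rule for a drug whose paediatric phase I dose-limiting toxicities included proteinuria (2.4.1).

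Appendix IV has a related weakness. Grams of protein per day equal UPC multiplied by grams of creatinine per day. A one-to-one rule therefore assumes about 1 g of creatinine daily, which is an adult-sized output. In a small child the rule reads too high. At stake is the correctness of a printed threshold and of a reference page that two parts of the protocol cite, not an efficacy conclusion.

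**Working it through.** **A. Entry limit (3.2.8.2c)**

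Inputs: 1000 mg/dL (3.2.8.2c) and the 3.5 g/24 h hold limit (5.4.5).

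- Unit conversion: 1000 mg/dL × 10 dL/L = 10,000 mg/L = 10 g/L.
- Volume at which a patient at the printed limit reaches the hold limit: 3.5 g ÷ 10 g/L = 0.35 L/day.
- Volume at which the printed limit equals 1000 mg/24 h: 1 g ÷ 10 g/L = 0.1 L/day. Above that, the printed limit is looser than the evident intent.
- Assumed urine volumes (the documents give none): 0.5, 1.0 and 1.5 L/day would allow up to 5, 10 and 15 g/24 h.

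**B. Appendix IV conversion**

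Reproducing its example: 90 mg/dL ÷ 30 mg/dL = 3. The ratio is right.

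The step to grams is: protein (g/day) = UPC × creatinine rate (mg/kg/day) × weight (kg) ÷ 1000.

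Rates are Appendix IV's 15 to 25 mg/kg/day. The weights are examples that I have assumed. The documents give no weights and no child creatinine rates, so adult rates are extrapolated.

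- One-to-one holds when rate × weight = 1000 mg/day: 1000/25 = 40 kg, 1000/20 = 50 kg, 1000/15 = 66.7 kg.
- Overstatement by the rule = 1000 ÷ (rate × weight).

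| Weight (assumed) | Creatinine, g/day | Overstatement | UPC 3 is really, g/24 h | UPC matching 1 g/24 h |
|---|---|---|---|---|
| 10 kg | 0.15–0.25 | 4.0–6.7 fold | 0.45–0.75 | 4.0–6.7 |
| 20 kg | 0.30–0.50 | 2.0–3.3 fold | 0.90–1.50 | 2.0–3.3 |
| 30 kg | 0.45–0.75 | 1.3–2.2 fold | 1.35–2.25 | 1.3–2.2 |
| 40 kg | 0.60–1.00 | 1.0–1.7 fold | 1.80–3.00 | 1.0–1.7 |

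A child rate below 15 mg/kg/day would widen the gap. At an assumed 10 mg/kg/day, UPC 3.5 in a 10 kg child is 3.5 × 10 × 10 ÷ 1000 = 0.35 g/24 h.

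**C. Does the conversion reach the hold rule?**

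The 5.4.5 screen is UPC of 1 or more, followed by a measured collection. A UPC below 1 can reach 3.5 g/24 h only above 3.5 ÷ 0.025 = 140 kg. The screen therefore sends practically every patient near the hold limit to a collection, and the decision is then made on measured grams.

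**The case against.** **The unit is an obvious misprint.** The limit is described as a 24-hour value, it sits beside UPC below 1, and it cites Appendix IV, so a sensible reader will take it as mg/24 h. No realistic misreading has been shown. That stands as to intent, and it is why the point is minor. It does not make the text right, since 3.2 asks for a literal reading.

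**Appendix IV is hedged.** It elsewhere says the two quantities are only roughly equal. But one line is unqualified, and a rough equality does not cover an error of several fold that always runs the same way in small patients.

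**The stronger reading.** A reader might infer that small children will be held off drug unnecessarily. Footnote 9 lets UPC follow prior proteinuria, 5.4.5 allows either test after restart, and no UPC hold or resume limit is printed, so a site might convert by Appendix IV. The documents do not support this as the main finding:

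- The 5.4.5 step from UPC of 1 or more to a collection is unconditional. It can be read to cover follow-up, and footnote 9 points to it.
- Nothing tells sites to convert UPC to grams for a dosing decision; both limits are in g/24 h.
- A child held under 5.4.5 must already have had a measured 3.5 g/24 h or more. On the rates above that is a UPC of about 14 to 23 at 10 kg and 7.0 to 11.7 at 20 kg.
- Such a hold would be unnecessary only against a flat 3.5 g/24 h. That limit is not scaled to body size and may itself be lenient for small children.

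What remains is an ambiguity in the follow-up wording, not a shown path to harm.

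**Conclusion.** The point holds at minor severity, in two parts.

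1. The 24-hour entry limit in 3.2.8.2c is wrong as printed. Literally it is 10 g/L, which exceeds the protocol's own hold limit at any urine volume above 0.35 L/day. This part needs no assumption beyond the unit.
2. Appendix IV's one-to-one conversion lacks a size condition that its own creatinine rates require. The fold errors rest on assumed weights and on adult rates extrapolated to children. The direction is firm: it overstates grams per day in small patients.

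The documents do not show that any patient was admitted on the literal limit or held because of the conversion. Neither part affects the objective response rate, the two-stage rule, type I error or power. SAP 4.3 records that the study was declared futile after stage 1 and that termination was approved, so the remaining value is a correct record and not carrying the text into another protocol.

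**What to change.** - **3.2.8.2c:** change the 24-hour limit to below 1000 mg/24 h.
- **Appendix IV:** state that UPC approximates g/24 h only when creatinine excretion is about 1 g/day, and must not be converted to grams in smaller patients. Add that hold and resume decisions use the measured 24-hour collection that 5.4.5 already requires when UPC is 1 or more. This restates the existing step and is not a new rule.

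The cost is two wording edits. A site that had been relying on UPC alone in follow-up might need an occasional extra collection, which is harder in young children.

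Two things are left alone as clinical decisions. After the unit is corrected, the 24-hour option will still be looser than UPC below 1 in a small child (last column of the table). And 3.5 g/24 h stays unscaled for body size.

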13.7 APPENDIX V: BLOOD PRESSURE LEVELS FOR CHILDREN BY AGE AND HEIGHT PERCENTILE

Blood pressure (BP) levels for BOYS

			Systolic Blood Pressure, mm Hg						Diasto	lic Blo	od Pre	ssure,	mm Hg		
Age	BP			Percei	ntile of	Height	t				Perce	ntile of	Height	t	
(years)	Percentile	5th	10th	25th	50th	75th	90th	95th	5th	10th	25th	50th	75th	90th	95th
1	95th	98	99	101	103	104	106	106	54	54	55	56	57	58	58
2	95th	101	102	104	106	108	109	110	59	59	60	61	62	63	63
3	95th	104	105	107	109	110	112	113	63	63	64	65	66	67	67
4	95th	106	107	109	111	112	114	115	66	67	68	69	70	71	71
5	95th	108	109	110	112	114	115	116	69	70	71	72	73	74	74
6	95th	109	110	112	114	115	117	117	72	72	73	74	75	76	76
7	95th	110	111	113	115	117	118	119	74	74	75	76	77	78	78
8	95th	111	112	114	116	118	119	120	75	76	77	78	79	79	80
9	95th	113	114	116	118	119	121	121	76	77	78	79	80	81	81
10	95th	115	116	117	119	121	122	123	77	78	79	80	81	81	82
11	95th	117	118	119	121	123	124	125	78	78	79	80	81	82	82
12	95th	119	120	122	123	125	127	127	78	79	80	81	82	82	83
13	95th	121	122	124	126	128	129	130	79	79	80	81	82	83	83
14	95th	124	125	127	128	130	132	132	80	80	81	82	83	84	84
15	95th	126	127	129	131	133	134	135	81	81	82	83	84	85	85
16	95th	129	130	132	134	135	137	137	82	83	83	84	85	86	87
17	95th	131	132	134	136	138	139	140	84	85	86	87	87	88	89

Instructions for using this BP Chart:

1. Measure the patient's blood pressure using an appropriate size cuff.

2. Select appropriate chart for a female or male patient.

3. Using the "age" row and "height" column determine if the BP is within the ULN.

4. See Section 5.1.2.5 for definition of dose limiting hypertension, Section 5.4.1 for management and grading of hypertension, and Section 4.1.5.1 for medical treatment of pazopanib related hypertension.

This table was taken from "The Fourth Report on the Diagnosis, Evaluation, and Treatment of High Blood Pressure in Children and Adolescents" PEDIATRICS Vol. 114 No. 2 August 2004, pp. 555-576.

Note: For patients \geq 18 yrs, ULN BP is 140/90 mmHg.

Blood pressure (BP) levels for GIRLS

		Systolic Blood Pressure, mm Hg							Diasto	lic Blo	od Pre	ssure,	mm Hg	J	
Age	BP	Percentile of Height								Perce	ntile of	Heigh	t		
(years)	Percentile	5th	10th	25th	50th	75th	90th	95 th	5th	10th	25th	50th	75th	90th	95th
1	95th	100	101	102	104	105	106	107	56	57	57	58	59	59	60
2	95th	102	103	104	105	107	108	109	61	62	62	63	64	65	65
3	95th	104	104	105	107	108	109	110	65	66	66	67	68	68	69
4	95th	105	106	107	108	110	111	112	68	68	69	70	71	71	72
5	95th	107	107	108	110	111	112	113	70	71	71	72	73	73	74
6	95th	108	109	110	111	113	114	115	72	72	73	74	74	75	76
7	95th	110	111	112	113	115	116	116	73	74	74	75	76	76	77
8	95th	112	112	114	115	116	118	118	75	75	75	76	77	78	78
9	95th	114	114	115	117	118	119	120	76	76	76	77	78	79	79
10	95th	116	116	117	119	120	121	122	77	77	77	78	79	80	80
11	95th	118	118	119	121	122	123	124	78	78	78	79	80	81	81
12	95th	119	120	121	123	124	125	126	79	79	79	80	81	82	82
13	95th	121	122	123	124	126	127	128	80	80	80	81	82	83	83
14	95th	123	123	125	126	127	129	129	81	81	81	82	83	84	84
15	95th	124	125	126	127	129	130	131	82	82	82	83	84	85	85
16	95th	125	126	127	128	130	131	132	82	82	83	84	85	85	86
17	95th	125	126	127	129	130	131	132	82	83	83	84	85	85	86

Instructions for using this BP Chart:

1. Measure the patient's blood pressure using an appropriate size cuff.

2. Select appropriate chart for a female or male patient.

3. Using the "age" row and "height" column determine if the BP is within the ULN.

4. See Section 5.1.2.5 for definition of dose limiting hypertension, Section 5.4.1 for management and grading of hypertension, and Section 4.1.5.1 for medical treatment of pazopanib related hypertension.

This table was taken from "The Fourth Report on the Diagnosis, Evaluation, and Treatment of High Blood Pressure in Children and Adolescents" PEDIATRICS Vol. 114 No. 2 August 2004, pp. 555-576.

Note: For patients \geq 18 yrs, ULN BP is 140/90 mmHg.

13.8 APPENDIX VI: PHARMACOKINETIC STUDY FORM

 COG Pt ID #_____ACC #_____SPONSOR Patient ID #_____

 Please do not write patient names on this form or on samples.

Confidential

Except for Cycle 1 Day 1, pre-dose samples should be collected between 22-26 hours after the previous dose of pazopanib.

Samples will be obtained as outlined in the tables below. Record the exact time the sample is drawn and the exact time that the dose of pazopanib was given.

CYCLE 1:

Day 1:

Body Surface Area: ° m ²	Dose: _ mg/m ²	Total Dose: _ mg
Date and time of dose given on Cycle 1, D	ay 1: Date:	Time: :
Day 15 (± 1):	(141	(M/DD/11)
Body Surface Area: ° m ²	Dose: _ mg/m ²	Total Dose: _ mg
Date and time of dose given on Cycle 1, D	ay 15 (± 1): Date:	Time: : M/DD/YY)

All patients not participating in Extended PK sampling:

Blood Sample		Scheduled Collection	Actual Date Sample	Actual Time Collected
No.	Time Point	Time	Collected	(24-hr clock)
1	Cycle 1, Day 1	Prior to dose		
2ª	Cycle 1, Day 15 (± 1)	Prior to dose		
3 ^a	Cycle 1, Day 15 (± 1)	3-4 hrs after dose		

Patients receiving powder suspension formulation and participating in Extended PK sampling:

			Actual Date	Actual Time
Blood Sample		Scheduled Collection	Sample	Collected
No.	Time Point	Time	Collected	(24-hr clock)
1	Cycle 1, Day 1	Prior to dose		
2	Cycle 1, Day 1	30 min after first dose		
3	Cycle 1, Day 1	1 hr after first dose		
4	Cycle 1, Day 1	2 hrs after first dose		
5	Cycle 1, Day 1	4 hrs after first dose		
6	Cycle 1, Day 1	6 hrs after first dose		
7	Cycle 1, Day 1	8 hrs after first dose		
10 ^a	Cycle 1, Day 15 (± 1)	Prior to dose		
11 ^a	Cycle 1, Day 15 (± 1)	30 min after first dose		
12 ^a	Cycle 1, Day 15 (± 1)	1 hr after dose		
13 a	Cycle 1, Day 15 (± 1)	2 hrs after dose		
14 ^a	Cycle 1, Day 15 (± 1)	4 hrs after dose		
15 a	Cycle 1, Day 15 (± 1)	6 hrs after dose		
16 a	Cycle 1, Day 15 (± 1)	8 hrs after dose		

Pazopanib dosing of either tablet or powder suspension must have continued uninterrupted and at the same dose level for at least 10 days prior to acquisition of the Cycle 1 Day 15 PK samples. If pazopanib dosing has been interrupted or modified <10 days prior to Cycle 1 Day 15, then the PK samples should be taken between Cycle 1 Day 15 and Cycle 1 Day 22 on a study day that meets the condition of at least 10 consecutive days of dosing at the same dose level. The Cycle 1 Day 15 PK kit should be used, and the actual date and time of sample

collections should be recorded in the eCRF.

SUBSEQUENT CYCLES:

For patients who continue to receive protocol therapy, PK sampling is also **required** prior to subsequent odd-numbered cycles. This sample may be taken between Day 22 of the previous even -numbered cycle to Day 1 of the odd-numbered cycle (e.g., between Day 22 of Cycle 2 and Day 1 of Cycle 3). Please record the actual Cycle and Day on which the sample was obtained. The timing of this sample should be between 22-26 hours after the previous dose of pazopanib. For samples collected in Cycle 3 and greater, record the date, time, and amount of the pazopanib dose administered on the study day prior to the blood sample collection in the area below For Cycle 3 pre-dose: Cycle # Day # Sample Collected: Date: Time: ____ : ____ (MM/DD/YY) Date and Time of Prior Pazopanib Dose: Date: Time: |__| : |_ (MM/DD/YY) Body Surface Area: | |°| | | m² Dose: |__|_|mg/m² Total Dose: | | | |mg Cycle # Day # Sample Collected: Date: _____ Time: ____ : ____ For Cycle 5 pre-dose: Time: |__| : | Date and Time of Prior Pazopanib Dose: Date: (MM/DD/YY) Body Surface Area: | |°| | | m² Dose: Total Dose: |__|_|mg $| | |mg/m^2$
 For Cycle 7 pre-dose:
 Cycle # _____
 Day # _____
 Sample Collected:
 Time: |___| : |___| Date: (MM/DD/YY) Date and Time of Prior Pazopanib Dose: Date: Time: | | |:| (MM/DD/YY) Total Dose: |__|_|mg Body Surface Area: | |°| | m² Cycle # ____ Day # ____ Sample Collected: For Cycle 9 pre-dose: Date: Time: |___| : |___| (MM/DD/YY) Date and Time of Prior Pazopanib Dose: Date: Time: ____ : | (MM/DD/YY) Body Surface Area: | |°| | | m² | $|mg/m^2$ Total Dose: | | | |mg Dose: For Cycle 11 pre-dose: Cycle # Day # Sample Collected: Date: Time: |__| : |__| (MM/DD/YY) Date and Time of Prior Pazopanib Dose: Date: Time: | | |:| (MM/DD/YY) Body Surface Area: | |°| | m² **Dose:** | | | |mg/m² Total Dose: | | | |mg Signature: Date:

(site personnel who collected samples)

Sample Collection, Handling, and Processing

- 1. Blood samples will be collected into tubes containing potassium EDTA as an anticoagulant and may be drawn from a central venous catheter.
- 2. The samples should be centrifuged at approximately 2500 x g at 5°C for 10 minutes. The resulting volume of plasma will be transferred in equal aliquots to two (2) corresponding pre-labeled polypropylene storage tubes. The tubes will be frozen in an upright position at -20°C until shipped to the laboratory for analysis.
- 3. Each tube must be labeled with the Sponsor study specific patient number, the study I.D. (ADVL1322/VEG116731), and the date and time the sample was drawn. Please also see the instructions in the Central Laboratory Services Manual (binder) that is provided with the initial start up PK kits from the same set of the same set.

A copy of this form along with a copy of the requisition form provided in the kits from should be sent with the samples. All samples should be batched and shipped with adequate amounts of dry ice. Shipments should be sent **Monday through Thursday only** for priority overnight delivery (do not ship on Friday) to the address listed in the PK kit supplied by

If this form will be used as a source document, the site personnel who collected the samples must sign and date this form below:

Signature:

(site personnel who collected samples)

Date::_____
